Statistical Analysis Plan

April 9, 2018

NCT04821245

ID: BRI IRB18-008

Defining Normal Postoperative Magnetic Resonance Imaging after Total Knee Arthroplasty

Human Subjects Protocol

Study Title: Defining Normal Postoperative Magnetic Resonance Imaging after Total Knee Arthroplasty

PRINCIPAL INVESTIGATOR: [name]
Department of Anesthesiology
Virginia Mason Medical Center
[name]
[contact]
[contact] (day)
[contact] (night and weekend)

SUB-INVESTIGATOR(S): C. [name]
Department of Radiology
Virginia Mason Medical Center
[contact]
[contact] (day)
[contact] (night and weekend)

[name]
Department of Orthopedic Surgery
Virginia Mason Medical Center
[contact]
[contact] (day)
[contact] (night and weekend)

Table of Contents-

A. Specific Aims.....	Page 1
B. Background & Significance.....	Page 1
C. Research Design & Methods (including analysis).....	Page 2
D. Protection of Human Subjects.....	Page 3
E. References/Literature Citations.....	Page 6

A. SPECIFIC AIMS

The purpose of this convenience sample observational study is to define normal magnetic resonance imaging (MRI) appearance of upper leg soft tissues and normal creatine phosphokinase (CPK) and aldolase levels after total knee arthroplasty (TKA). This knowledge is crucial for proper diagnosis and further understanding of the recently described sentinel complication of presumed local

anesthetic-induced myotoxicity after TKA in patients who received a continuous adductor canal block (CACB) for postoperative analgesia.

This study aims primarily to define quadriceps muscle appearance on MRI in 10 asymptomatic volunteers two days after undergoing uneventful TKA. The secondary aim is to investigate baseline and postoperative CPK levels coincident with TKA.

B. BACKGROUND, SIGNIFICANCE, and PRELIMINARY STUDIES

Local anesthetics consistently induce myotoxicity in animal models and in up to 0.5% of humans after ophthalmologic nerve blocks, yet clinically apparent myotoxicity in patients undergoing other peripheral nerve blocks was believed heretofore to be nearly non-existent.¹ This changed after introduction of CACB at Virginia Mason Medical Center when 4 patients developed symptoms, MRI findings, and neurophysiologic testing compatible with local anesthetic-induced myotoxicity.² In short order, other cases were reported from the Swedish Orthopedic Institute,³ and anecdotally from practices throughout the United States. Furthermore, a recent retrospective review of MRIs obtained at VMMC for various indications within a week of TKA failed to identify a consistent pattern of MR findings that might have defined "normal MRI appearance" after TKA (BRI: 16092).⁴

These sentinel complications have resulted in major morbidity for the affected patients. After a normal early postoperative course, the patients rapidly developed flaccid quadriceps muscles and the inability to lift the operative lower extremity against gravity, with consequent halting of their rehabilitative trajectory. While fortunate patients recovered fully or nearly so after weeks to a few months as the unaffected myoblasts regenerated, less fortunate patients have never recovered to baseline.

Because non-ophthalmic myotoxicity has never been described to this degree in humans, little is known about its etiology, diagnosis, and treatment. Definitive diagnosis of myositis requires muscle biopsy, but this invasive and expensive intervention is unlikely to occur. All patients in our series² had MRI signals consistent with edema and inflammation, but non-specific for myositis. However, the radiologic literature is silent with regard to what constitutes normal MRI findings immediately after TKA. Consequently, the MRI pathology that we observed, while clearly demonstrating inflammatory changes in the anterior compartment of the upper leg, could conceivably represent normal postoperative findings. We have attempted to study this question by retrospectively reviewing MRIs of patients who underwent leg MRI within a week of TKA.⁴ Although we could identify several patients in that cohort with clinical presentations consistent

with undiagnosed myotoxicity, we were unable to confidently discern pathological findings versus 'normal' postoperative changes on imaging.

C. RESEARCH DESIGN AND METHODS (including data analysis)

- Twenty volunteers of various age and sex that are scheduled for unilateral TKA by [name] (VM orthopedic surgeon) will be approached by [name] to ascertain their willingness to volunteer for this study
- Identified patients will be consented for study participation by the PI ([name]) at least 24 hours prior to their surgery
- All patients will be cared for under the standard VMMC TKA clinical pathway, which includes a 2 day CACB
- If their postoperative course has been normal, the 20 volunteers will undergo unilateral thigh MRI with gadolinium based MRI contrast prior to discharge home on the morning of postoperative day 2. These patients will have pre- and post-op CPK and aldolase levels analyzed.
 - Patients will have their hip and knee motor strength assessed for baseline pre-surgery and again prior to MRI to ensure there is no evidence of atypical muscle weakness.
 - To reduce the likelihood of residual local anesthetic, the CACB infusion will be turned off at 0500 the morning of hospital Day 2
 - The MRI will not occur before 0700 of that day
 - Pre-operative CPK and aldolase will be included with the subject's routine pre-operative blood work
 - Post-operative CPK and aldolase will be drawn the morning of hospital day 2 prior to discharge
- Leg MRIs will be graded using a standardized checklist (developed for our previous retrospective study) by a radiology resident who is unaware of the findings from our retrospective assessment of symptomatic subjects. The resident will be supervised by [name].
- The radiologist's objective scoring of the MRI, together with the pre- and post-operative CPK and aldolase levels, will be entered into a password-protected spreadsheet. The subjects will be identified initially by their medical record number (MRN). Prior to sharing these results with our colleague [name] (Puget Sound VA Health System), the MRNs will be deleted. [name] role in the study includes design and writing, but she will have no interaction with the subjects.
- This is an observational study in which the convenience sample of 20 volunteers is dictated by the grant monies procured. As an observational study, there will be no statistical analysis.

D. PROTECTION OF HUMAN SUBJECTS

1. RISKS TO THE SUBJECTS:

a. Human Subject involvement and characteristics

- The TKA patients who volunteer for this study will have pre- and post-operative CPK and aldolase analysis and unilateral leg MRI with radiologic contrast the morning of hospital day 2
- The 20 volunteers will be between age 50 and 75. They will meet inclusion and exclusion criteria. Subjects will include both sexes
- Volunteers can withdraw from the study at any time

ENROLLMENT

-Collaborating sites

None

INCLUSION/EXCLUSION CRITERIA

Inclusion criteria

- Anticipated unilateral TKA performed under the standard VMMC TKA pathway
- Subjects will be operated by a single surgeon ([name]) to eliminate possible confounders related to surgical technique
- Planned 2 night stay at VMMC
- Subjects must be willing to volunteer for MRI study and CPK blood draws
- Age 50 to 75 years; either sex

Exclusion criteria

- Any contraindication to the use of spinal anesthesia or ACB-based analgesia
- Operative tourniquet time in excess 120 min and/or inflation pressure in excess of 300 mmHg
- History of muscle wasting or related disease
- History of pre-existing neurologic condition affecting the lower extremities
- Allergy to gadolinium based MRI contrast.
- Renal insufficiency
- Standard contraindications to MRI examination
- Children are excluded. They generally do not receive TKA

TOTAL PLANNED ENROLLMENT

Targeted/Planned enrollment: number of subjects (n= 20)

Ethnic Category	Sex/Gender		
	Females	Males	Total
Volunteers will be recruited without regard to sex or ethnic category. Although we will strive to have some mix of male and female volunteers, there is no set number that we wish to attain. Reported cases of myotoxicity have occurred in both sexes, but more males, as is consistent with the TKA population dynamic.			

A. Sources of Materials:

- CPK and aldolase blood analysis and unilateral leg MRI with their results
- Virginia Mason radiology personnel and laboratory personnel will handle the CPK and aldolase specimens and MRI images in the usual fashion, which includes the patient's name, MRN.
- Results of the above exams will be entered into a password-protected spreadsheet that will be accessible only to the PI. When the final data are sent to the Sub-Is for analysis, the patient's MRN will be removed such that the only remaining identification will be "Subject 1, Subject 2, etc."

B. Potential Risks:

- The potential risk associated with the MRI exam is the rare occurrence of allergic reaction to gadolinium based MRI contrast.
- The potential risk of CPK and aldolase analysis is that inherent to phlebotomy, i.e., rare chance of infection, bruising, mild discomfort
- Potential social risks include breach of confidentiality or privacy
- There are no alternative treatments available

C. Adequacy of Protection Against Risks:

1. Recruitment and Informed Consent

-Potential volunteers will be identified by [name] during his pre-surgical examination process. The volunteers will then be consented by [name] in person, when possible, or by phone. The consent process will take place at least one day prior to the surgical procedure. As noted, children and special classes will not be included in the study. Consent will be

documented using approved BRI consent forms – written and signed, with copies for subject and research study archives.

2. Protection against Risk:

- Standard assessment of allergy or MRI-associated risk prior to MRI study
- Standard care during phlebotomy
- Referral to psychological counseling if indicated
- All data will be de-identified completely except for the linkage of the subject's MRN to their data set. As noted, the MRN will be removed from the spreadsheet when it is sent to co-investigators for analysis
- The data spreadsheet will reside on [name] password-protected computer and will itself be password protected.

D. Potential Benefits of the Proposed Research to The Subjects And Others.

- There is no benefit to the subject for participation in this study

E. Importance of the Knowledge to Be Gained

- The results of this study should define the effectiveness of MRI and/or CPK and aldolase as diagnostic tools in future patients with suspected local anesthetic-induced myotoxicity
- For this previously unknown complication, new knowledge is critical for both understanding the proper diagnosis and for complication management. We have tried other routes to understand the diagnostic paradigm, to no avail. The low risk and inconvenience of postoperative MRI and CPK studies will facilitate further knowledge related to this complication.

F. Subject Safety and Minimizing Risks

- [name] will contact patients on postoperative day 2 to ensure their desire to continue with the study
- [name] will monitor adverse events and their reporting. Other than the rare allergic reaction to radiologic contrast, no adverse events are anticipated

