Because non-ophthalmic myotoxicity has never been described to this degree in humans, little is known about its etiology, diagnosis, and treatment. Definitive diagnosis of myositis requires muscle biopsy, but this invasive and expensive intervention is unlikely to occur. All patients in our series had MRI signals consistent with edema and inflammation, consistent with myositis. However, the radiologic literature is silent with regard to what constitutes normal MRI findings immediately after TKA. Therefore, the MRI pathology that we observed, while clearly demonstrating inflammatory changes in the anterior compartment of the leg, could conceivably represent normal postoperative findings. We have attempted to study this question by retrospectively reviewing MRIs of patients who underwent leg MRI within a week of TKA. While we could identify several patients with clinical presentations consistent with undiagnosed myotoxicity, we were unable to confidently discern pathological findings versus 'normal' postoperative changes on imaging.

**b. If applicable, please describe statistical methods of the research and plans for analysis of the data (i.e. planned statistics, justification of sample size, etc.).**

Observational convenience sample, therefore N/A

**c. Are there any alternative treatments to participating in this research (e.g., standard of care treatment, etc.)?** N

If yes, describe. Any standard treatment that is being withheld must be disclosed. This information must be included in the consent form.

d. Can subjects receive alternative treatment outside of enrolling in this study? N/A

e. Will subjects be followed after their participation is complete? N

If yes, explain why and describe how:

f. Is this a cooperative study (e.g. UW, FHCRC is IRB of record)? N

(If yes, answer the questions below. If no, proceed to the next section. [Click here for more information.](#))

i. Has this study been approved by the IRB of record? (NOTE: BRI IRB cannot review any COOP study not currently approved by the IRB of record)

If yes, when did the initial approval for this study occur?

ii. Has this study undergone Continuing Review (CR) at the IRB of record?

If yes, what are the current approval dates?

iii. Will there be any costs to VM for study procedures (e.g. lab costs, etc.)?

If yes, how will these costs be paid to VM? (e.g., direct billing to your grant, etc.)

iv. Will potential subjects from VM be approached?

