 **Other, explain below:**

From VMMC orthopedic surgical patients scheduled for TKA. Initial willingness to participate in the study will be ascertained by [name] or his physician assistant.

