 **Other, explain below:**

From VMMC orthopedic surgical patients scheduled for TKA. Initial willingness to participate in the study will be ascertained by [name] or his physician assistant.

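### The normal reference set is a convenience sample with no set order of approach and no record of who was passed over or declined; consecutive invitation with a log would close that gap

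*SAP*

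**What the plan says.** The purpose is to define normal thigh MRI appearance and normal CPK and aldolase after knee replacement (SAP section A; amended application, item 2). The sample is called a convenience sample in SAP sections A and C and in item 5b of the application.

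- **Number.** SAP section C: "This is an observational study in which the convenience sample of 20 volunteers is dictated by the grant monies procured". It continues: "As an observational study, there will be no statistical analysis". Item 5b, which asks for statistical methods and sample-size justification, is answered: "Observational convenience sample, therefore N/A".
- **Who finds candidates.** SAP section D, Recruitment and Informed Consent: "Potential volunteers will be identified by [name] during his pre-surgical examination process".
- **Who approaches them.** Application item 7c: "Initial willingness to participate in the study will be ascertained by [name] or his physician assistant". Item 3a instead speaks of the centre's orthopedic surgeons in the plural. Consent is then taken by the principal investigator.
- **Mix.** SAP section D, Total Planned Enrollment: "Although we will strive to have some mix of male and female volunteers, there is no set number that we wish to attain".
- **Pool and time.** Application items 6e and 6f give 1000 eligible patients per year at the centre and 3 months of accrual. The inclusion criteria in both documents restrict entry to one surgeon.

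Neither document sets a consecutive or random order, asks for a screening log, or asks for counts of patients not approached or declining.

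**The concern.** In a study whose product is a description of normal, the choice of subjects largely determines the result. Grant money limits how many scans can be bought; it does not call for a discretionary choice of who is scanned. Candidates are identified at the pre-surgical examination, where the clinician sees their general condition, and the plan wants subjects whose course turns out normal. Approaching mainly those expected to recover easily would be a natural habit, and nothing in the plan would stop it or show it.

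If that happened, ordinary postoperative change could be under-represented, and later patients with ordinary change could be read as abnormal. The SAP's background section says the team's retrospective review could not separate pathology from normal postoperative change, so this is the error the study is meant to resolve. Both documents also expect the results to define how useful MRI and the enzymes are for diagnosis.

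**Working it through.** **1. The plan's own figure.** The number 20 comes from the grant. No precision target, standard deviation, error rate or dropout allowance is given, so there is no calculation to reproduce.

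**2. The pool.** From application items 6e and 6f: 1000 × 3/12 = 250 in three months, and 20/250 = 8%. But 1000 is for the whole centre. If the surgeon's share is s (not stated, so assumed), the pool is 250 × s and the scanned fraction is 20/(250 × s).

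| Assumed share | Pool in 3 months | 20 as % of pool |
|---|---|---|
| 100% | 250 | 8% |
| 50% | 125 | 16% |
| 25% | 62.5 | 32% |
| 10% | 25 | 80% |
| 8% | 20 | 100% |

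The room for choice may be large or nil.

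**3. What selective approach could do (illustration; all inputs assumed).** Let Y be a marker such as log CPK, standard normal in all normal patients. Let X be the approacher's expectation of a poor course, with correlation ρ to Y: Y = ρX + √(1 − ρ²)·E. Leave out the top 10% or 25% on X and find the 97.5th percentile of Y among the rest (2,000,000 draws). Without selection it is 1.96 SD, exceeded by 2.5% of normals.

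| ρ | Top 10% left out | Top 25% left out |
|---|---|---|
| 0 | 1.96 SD (2.5% above) | 1.96 SD (2.5%) |
| 0.3 | 1.87 SD (3.1%) | 1.79 SD (3.7%) |
| 0.5 | 1.77 SD (3.8%) | 1.61 SD (5.4%) |
| 0.7 | 1.62 SD (5.3%) | 1.36 SD (8.7%) |

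Other patterns act differently. At ρ = 0.5, leaving out the lowest 25% raises the upper limit to 2.08 SD. Taking only the two outer quarters widens the central 95% interval from 3.92 to 4.27 SD.

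For a yes/no MRI finding, suppose the true prevalence is 20% and selection halves it. The chance of seeing none in 20 goes from 0.8²⁰ = 1.2% to 0.9²⁰ = 12.2%.

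**4. What remains with perfect sampling.** For n = 20 independent normals, the expected share of the population inside the observed minimum and maximum is (n − 1)/(n + 1) = 19/21 = 90.5%. The chance that this range covers at least 95% is 1 − (20 × 0.95¹⁹ × 0.05 + 0.95²⁰) = 26%. A finding present in 10% of normals is missed altogether with probability 0.9²⁰ = 12.2%; one present in 5%, with probability 0.95²⁰ = 35.8%.

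**5. Feasibility of consecutive invitation.** Invitations needed = 20/(acceptance × share scanned after a normal course), rounded up. Neither rate is in the documents.

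| Acceptance | Normal course | Invitations |
|---|---|---|
| 90% | 100% | 23 |
| 50% | 100% | 40 |
| 50% | 90% | 45 |
| 30% | 100% | 67 |
| 20% | 80% | 125 |

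Forty-five invitations fit a pool of about 62 (25% share) but not one of 25 (10% share). The change fits 3 months in many of these cases, not all.

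**The case against.** A reader might infer that the surgeon's team hand-picks patients expected to do well, at about 1 in 12 of those eligible, and that the normal range will therefore be too narrow by a calculable amount. The documents do not support that.

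- No passage describes anyone being passed over because of expected outcome. The SAP asks for volunteers of various age and sex and for recruitment without regard to sex or ethnic category. This stands: the gap is an absent safeguard, not a demonstrated practice.
- The 1 in 12 takes the centre's volume for one surgeon's. This stands too.
- The correlations in step 3 have no source in the documents. The illustration concerns an enzyme, which is a secondary aim; the primary aim is a graded MRI appearance, and no percentile limit is planned. Hence step 3 shows a mechanism, not a magnitude.
- Part of the apparent selection is legitimate eligibility. Muscle-wasting and lower-limb neurologic exclusions, strength testing before MRI and the normal-course condition define the target population and would remain.
- Strict ordering has practical limits. MRIs are booked as scheduled cases, the SAP's tourniquet exclusion is known only after surgery, and no HIPAA waiver is requested, so individual data on non-consenters are not clearly covered.

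These points limit the claim and shape the remedy. They do not supply a reason for leaving the order of approach open or for keeping no count of those approached.

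**Conclusion.** The point holds as a design weakness worth correcting. The reference set comes from one surgeon's patients, with the order of approach left to discretion and no record of those not approached or declining. Its representativeness therefore cannot be assured beforehand or judged afterwards. Too narrow a range is one possible consequence; a shifted or wider one is also possible. No size can be attached, because the surgeon's share, the acceptance rate and any link between the approacher's expectation and the findings are all unstated.

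Consecutive invitation is less open to bias at the same number of scans. It removes staff choice only: patients still select themselves, and the imprecision of 20 subjects is untouched.

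**What to change.** In SAP sections A and C and application item 5b, describe the sample as consecutive rather than convenience. Add the rule to SAP section C and application item 7a, along these lines:

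*Every patient of the study surgeon who meets the criteria known before surgery will be invited in order of surgery date, skipping only for a logged reason such as no MRI slot, until 20 scans are obtained. A log without identifiers will record the numbers eligible, invited, declined, excluded after surgery and not scanned, with reasons, and will be reported with the results.*

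Align item 3a (surgeons in the plural) with item 7a. Reconcile the target number in the same edit: SAP section A has "This study aims primarily to define quadriceps muscle appearance on MRI in 10 asymptomatic volunteers", against 20 in SAP sections C and D, and item 3a of the original application also has 10.

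**Cost.** The number of scans and blood tests stays at 20. The team gives up discretion over whom to approach, a minor IRB amendment is needed, and someone must keep the log. Accrual may run past 3 months if acceptance or the surgeon's volume is low. Keeping the log to counts and reasons avoids collecting individual data on patients who have not consented.

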## 2. Purpose

**Describe the purpose for the proposed project as well as the hypotheses/research questions to be examined.**

This study aims to define normal quadriceps imaging in 20 asymptomatic volunteers one to two days after undergoing TKA. A secondary aim is to investigate alterations in creatine phosphokinase (CPK) and aldolase levels coincident with TKA. The aim of this observational study is to define what constitutes a normal MRI appearance and normal CPK / aldolase alterations in postoperative TKA patients. This knowledge is crucial for proper diagnosis and further understanding of this sentinel complication.

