**4. Study Duration**

**What is the anticipated start date and duration of the proposed study?**

We plan to start immediately after IRB approval. We anticipate all 20 volunteers should be recruited and studied within a 3 month period

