Because non-ophthalmic myotoxicity has never been described to this degree in humans, little is known about its etiology, diagnosis, and treatment. Definitive diagnosis of myositis requires muscle biopsy, but this invasive and expensive intervention is unlikely to occur. All patients in our series had MRI signals consistent with edema and inflammation, consistent with myositis. However, the radiologic literature is silent with regard to what constitutes normal MRI findings immediately after TKA. Therefore, the MRI pathology that we observed, while clearly demonstrating inflammatory changes in the anterior compartment of the leg, could conceivably represent normal postoperative findings. We have attempted to study this question by retrospectively reviewing MRIs of patients who underwent leg MRI within a week of TKA. While we could identify several patients with clinical presentations consistent with undiagnosed myotoxicity, we were unable to confidently discern pathological findings versus 'normal' postoperative changes on imaging.

**b. If applicable, please describe statistical methods of the research and plans for analysis of the data (i.e. planned statistics, justification of sample size, etc.).**

Observational convenience sample, therefore N/A

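### The plan sets out to define normal MRI and enzyme findings after knee replacement but disclaims statistical analysis and names no estimate or measure of uncertainty

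*SAP*

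**What the plan says.** **Analysis.** SAP section C, whose heading promises data analysis, explains that grant money set the sample of 20 and then states: "As an observational study, there will be no statistical analysis". Question 5b of the protocol form asks for statistical methods, analysis plans and sample size justification. The answer is "Observational convenience sample, therefore N/A", in the initial form and unchanged in the amended one.

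**Purpose.** The amended form (section 2, Purpose) aims to "define what constitutes a normal MRI appearance and normal CPK / aldolase alterations in postoperative TKA patients". SAP section A likewise speaks of normal MRI appearance and normal enzyme levels. SAP section D, on the importance of the knowledge, expects the results to show how well MRI and the enzymes work as diagnostic tools in later patients with suspected myotoxicity.

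**Data.** SAP C has the MRIs graded on a standardized checklist. It enters the "objective scoring of the MRI, together with the pre- and post-operative CPK and aldolase levels" in a spreadsheet. SAP D says, under sources of materials and again under protection against risk, that the data then go to sub-investigators and co-investigators for analysis. No method is named.

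**Sample size.** The SAP's primary aim is to "define quadriceps muscle appearance on MRI in 10 asymptomatic volunteers two days after undergoing uneventful TKA". The amended Purpose is to "define normal quadriceps imaging in 20 asymptomatic volunteers one to two days after undergoing TKA", and its section 4 says "We anticipate all 20 volunteers should be recruited and studied within a 3 month period".

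**The concern.** The stated reason does not support the omission. A descriptive study needs no test, but to define normal is to estimate something: how often each MRI finding occurs in uncomplicated patients, where postoperative enzymes lie, and how far they move from baseline. Followed literally, the plan yields grades and enzyme values with no stated estimate and no indication of how firmly 20 people fix it.

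What is at stake is the intended use. A clinician could treat a finding never seen in this sample as abnormal, or treat the highest observed CPK as an upper limit of normal. The amended form (3c(i)) says that enzyme testing around knee replacement is not standard care, so a future patient may have no baseline. Postoperative levels therefore need their own summary as well as the change.

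**Working it through.** **Inputs.** N = 20 from SAP C and from planned enrollment in SAP D; N = 10 from the SAP's primary aim. The documents give no alpha, power, SD, event rate or precision target. There is thus no figure of the plan's own to reproduce: 20 is a budget figure. The 95% level and the independence of subjects are assumptions made here.

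**1. MRI finding, exact (Clopper-Pearson) two-sided 95% interval.** For 0 of N the upper limit is 1 − 0.025^(1/N).
- N = 20: 1 − 0.025^(1/20) = 16.8%.
- N = 10: 1 − 0.025^(1/10) = 30.8%.
- 20 of 20: lower limit 0.025^(1/20) = 83.2%.
- 1 of 20: 0.1% to 24.9%.
- 10 of 20: 27.2% to 72.8%.

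**2. Chance that a real finding is never seen.** If it is present in a share p of normal patients, the chance is (1 − p)^N. With p assumed to be 10%, 0.9^20 = 0.122, or 12%.

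**3. Highest of 20 enzyme values as an upper limit.** The chance that all 20 fall below the true 95th percentile is 0.95^20 = 0.358, or 36%. No distribution is assumed beyond a continuous one.

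**4. Minimum-to-maximum range.** Its average coverage of the population is (N − 1)/(N + 1): 19/21 = 90.5% at N = 20 and 9/11 = 81.8% at N = 10.

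**5. Interval for the median postoperative level.** At N = 20, the 6th to 15th ordered values cover the true median with probability 1 − 2·P(Bin(20, ½) ≤ 5) = 1 − 2 × 21,700/1,048,576 = 95.9%. A distribution-free interval is therefore available.

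**6. Paired post/pre change.** The 95% half-width is t(0.975, 19)/√20 = 2.093/4.472 = 0.468 SD. If the SD of the within-subject log ratio were 0.4 to 0.8 (an assumption, for illustration), the interval for a geometric mean ratio would be the estimate multiplied and divided by exp(0.468 × 0.4) = 1.21 to exp(0.468 × 0.8) = 1.45.

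**7. The two sample sizes.** Ten appears in the SAP's primary aim and in Procedures 3a of the initial form. Twenty appears in SAP C, in SAP D, in sections 4 and 6a of both forms, and in the amended Purpose. The matching clause in the amended Procedures 3a is blacked out and settles nothing either way.

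**The case against.** The fairest reply is that the SAP sentence means no inferential statistics. Section C is headed as including data analysis, and SAP D twice sends the data to colleagues for analysis, so some description was probably intended. This has force. A reader might infer that the plan forbids even descriptive reporting; those passages do not support so strong a reading. But they name no summary, so the gap remains.

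A second reply is that intervals lend false precision to a single-surgeon convenience sample selected for a normal course, and that anyone given n/N can compute them. It is true that they cover sampling error only, and the plan should say so. But n/N is not promised either, and no reader can derive an interval for the enzyme levels unless individual values are reported.

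Third, the protocol revision dated 5.29.18, the MRI Data Sheet and the Study Data Sheet are listed as attachments but are not among the supplied documents, and one of them might hold a plan. The point is therefore limited to the supplied text. The amended form, submitted on the date that the revision carries, still answers N/A.

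A reader might also infer that 20 is too few, or that only 10 people will be imaged. Neither follows. The convenience sample and its budget basis are openly declared, no precision target exists to miss, and most statements of the sample size, including the SAP's enrollment target, say 20.

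**Conclusion.** The point holds for the supplied text: the stated aim requires estimates, and the plan names none and gives no measure of their uncertainty. It should be fixed, but it is not a fault in the design. Being observational excuses the absence of a test and a power calculation, and no more.

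The size of the uncertainty left unstated is material. At N = 20, a finding seen in nobody is compatible with a prevalence of up to 16.8% (upper end of a two-sided exact 95% interval; the one-sided 95% bound, 1 − 0.05^(1/20), is 13.9%). The sample maximum falls short of the true 95th percentile 36% of the time. These figures assume independent subjects and all 20 measured. Only the illustrative ratio factors depend on an assumed SD, and the conclusion does not rest on them.

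The conflict between 10 and 20 is a separate consistency error. It matters here because it nearly doubles the upper limit for an unseen finding, from 16.8% to 30.8%.

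**What to change.** Replace the sentence in SAP C, and the N/A in protocol 5b, with:

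> Analysis is descriptive, with no hypothesis tests. N is the number actually imaged or sampled, reported with the number enrolled and the reasons for any not imaged. MRI checklist items: n/N with exact 95% CI. Graded items: counts per category, with exact 95% CI for the proportion in each category. Postoperative CPK and aldolase: median with distribution-free (order-statistic) 95% CI, and range, stated to be provisional and not a reference limit. Within-subject post/pre change: a paired summary with 95% CI, for example the geometric mean ratio on the log scale. If measurements fall on both postoperative day 1 and day 2, results are also shown by day. Intervals reflect sampling error only, and asymptomatic volunteers cannot inform sensitivity.

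The number actually imaged is specified because SAP C makes imaging conditional on a normal course and SAP D allows withdrawal. The split by day is there because the amended form allows one to two days where the SAP says two.

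Separately, reconcile the sample size: the SAP's primary aim should agree with the 20 in SAP C and D.

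**Cost.** One paragraph in two places, one number in the SAP, and a few hours' analysis of data that the study already plans to collect. Which items are graded must be settled from the MRI Data Sheet. The downside is that the intervals will be visibly wide at N = 20.
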